2.6 Radiation Therapy

Preclinical studies in melanoma and breast cancer cell lines and animal models have demonstrated that riluzole enhances the effectiveness of radiation therapy. To mimic brain metastases observed in melanoma patients, Wall et al developed an intracranial orthotopic transplant model of human melanoma.³³ They injected C8161-luciferase expressing cells intracranially into immunodeficient nude mice and monitored tumor cell establishment using luminescent imaging. Upon initial detection, animals were imaged bi-weekly to determine if riluzole could further sensitize orthotopic tumors to the effects of radiation therapy. The results in the intracranial model show that riluzole and irradiation alone resulted in decreased luminescence compared to vehicle treated alone (Figure 2.7). The combination of riluzole and irradiation resulted in enhanced reduction in tumor cell growth as suggested by luminescent signal detected. Similar outcomes were seen in a glioma model.

[figure not shown]
[figure not shown]

Figure 2.7. Intracranial transplants of human melanoma cells: Left: Week1: C8161-luc+ human melanoma cells were introduced into the brains of nude mice. Once luminescent signal was detected, animals were separated into groups and treated with either DMSO (Veh) or riluzole (Ril, 10 mg/kg), localized ionizing radiation (IR, 4 Gy) or a combination of the two (Ril+IR). Animals were terminated after 4 weeks of treatment. Images of animals showing initials and terminal images (**Left: Week 1, Middle: Week 4**). **Right:** The intensities of the emitted signal were quantified. The data were expressed as photon flux (photons/s/cm²/steradian, where steradian refers to the photons emitted). The background photon flux was subtracted from the signal intensities measured at the same site. Data were normalized to peak signal intensity of each time course.

2.7 Rationale

A key reason for resistance to immune checkpoint blockade is the lack of immune infiltrate in the tumor. In patients with metastatic melanoma, responses to PD-1 inhibitors are more frequent with an inflamed tumor microenvironment, distinguished by high numbers of TILs, high PD-L1 expression, and increased gene expression of the immune-related profile. Thus, adjunct agents that can increase immune infiltration in the tumor microenvironment, or convert a “cold” tumor into a “hot” tumor, are rational combination strategies. In tumors devoid of infiltrating lymphocytes (immune desert), trilorizole treatment may inhibit release of the exosomes and decrease TAMs, allowing lymphocytes into the tumor-stromal interface, thereby, enhancing the antitumor activity of immune checkpoint inhibitors. This hypothesis is supported by preclinical observations using an immunocompetent mouse model of melanoma, which demonstrates that the combination of

troriluzole + PD-1 blocking antibody inhibited the outgrowth of tumors better than either agent alone (Fig. 2.5).

There is an increasingly recognized intersection between antiangiogenic agents and immunotherapy.²⁵ We have shown that riluzole decreases VEGF levels and increase the immune infiltrate in tumor specimens from melanoma patients.²⁴ Others have shown that anti-angiogenic therapy can increase the efficacy of checkpoint blockade in uterine cancer and kidney cancer.²⁷⁻²⁹ There are numerous ongoing clinical studies in various cancers using a similar rationale, combining immune checkpoint blockade with either an anti-angiogenesis agent (e.g. bevacizumab, ramucurimab), or a macrophage-directed agent (e.g. CSF1 antibody, IPI-549). However, our approach is unique in two ways: 1) that troriluzole is a pro-drug of a well-known entity riluzole that has been FDA-approved for a non-oncology indication for over two decades, and therefore the safety track record is superior, and 2) riluzole crosses the blood-brain barrier and synergizes with radiation therapy, making it well-suited for study in brain metastases.

Despite recent advances, the care of patients with brain metastases due to melanoma remains very challenging. The FDA has called for inclusion of patients with brain metastases in trials of new agents, especially for diseases but commonly involve the CNS, and welcomed applications to expand an indication to include brain metastases.³⁴

Taking ipilimumab and nivolumab as the new standard of care for treatment of small asymptomatic melanoma brain metastases, the randomized phase 2 study described herein will attempt to build on the success of this regimen with the addition of troriluzole. The starting dose of troriluzole was determined in the phase 1b study with nivolumab. Patients in both arms may receive brain-directed stereotactic radiotherapy as needed. The rationale to include stereotactic radiosurgery in this trial is that it is standard of care to radiate isolated brain metastases and continue systemic therapy if it is otherwise effective, as was done in the Checkmate 2004 study.³ As there is preclinical synergy with radiation therapy with troriluzole this is something we will to investigate further in this trial in a subset analysis.

2.8 Correlative Studies Background

The primary goal of the correlative science is to obtain an understanding of the effects of the three-drug regimen vs. the two-drug regimen upon anti-cancer immunological activity. To that end, this study will include the following correlative studies:

- IHC on archival and fresh tumor samples. Tumors from patients who respond favorably to checkpoint blockade therapy showed higher pre-existing numbers of CD8, PD-1, and PD-L1 expressing cells in the tumors and at the invasive tumor margin (tumor-stroma interface) compared to non-responders.^{35,36} Response rate are often observed to be approximately 3 times higher in patients with tumors expressing high levels of PD-L1. IHC will be used to determine GRM1 expression, PD-L1 expression, the degree of TILs, and other immune effector cells, and on-treatment biopsies will be examined for change in TILs and decrease in signal transduction in key pathways (e.g. MAPK, Pi3K/AKT) and evidence of apoptosis (cleaved caspases). We hypothesize that nearly 100% of melanomas will have GRM1

overexpression.

- Flow cytometry on PBMCs. Immunophenotypic analysis of immune cells and markers will be assessed by multiparameter flow cytometry. We hypothesize that responders will display more favorable T cell population ratios, markers of activation, and differentiation, and fewer MDSCs.
- Multiplex cytokine analysis on serum and CSF. We hypothesize that responders will demonstrate a decrease in the expression of VEGF, IL-8, CD34, CCL2, and M-CSF.
- Gene expression analysis by Nanostring on blood and tumor samples. We hypothesize that responders will have a higher immune-related gene expression profile. We hypothesize there will be a decrease in oxidative phosphorylation genes post-treatment.
- Tumor genomic profiling. We will determine if activating mutations in B-RAF or N-RAS, or PTEN inactivation (or activating B-RAF mutations and PTEN inactivation together) in the pre-treatment tumor samples correlates with response to therapy.
- Exosome analysis. We will examine exosome contents and hypothesize that post-treatment serum samples will contain fewer suppressive cytokines than pre-treatment samples.

3. PARTICIPANT SELECTION

3.1 Eligibility Criteria

- 3.101* Participants must have histologically or cytologically confirmed melanoma. All melanoma subtypes are included, except for ocular melanoma.
- 3.102* Participants must have measurable disease in the brain (intraparenchymal brain metastases), defined as at least one lesion that can be accurately measured by MRI in at least one dimension as ≥ 5 mm and ≤ 3 cm in longest diameter. See Section 11 (Measurement of Effect) for the evaluation of measurable disease. Measurable disease in the extracranial compartment (body) is not required. Measurable lesions may not have received previous treatment with radiation therapy. Prior stereotactic radiation therapy or SRT (e.g. GammaKnife, CyberKnife) is allowed for lesions other than the lesions selected as measurable target lesions. Prior craniotomy with resection of brain metastases is allowed.
- 3.103* Participants are allowed, but not required to have received prior systemic treatment with anti-PD-1 therapy (e.g. pembrolizumab, or nivolumab) in any setting (neoadjuvant, adjuvant or metastatic). Prior anti-CTLA-4 monotherapy is allowed (e.g. ipilimumab). Prior targeted therapy (e.g.

BRAF inhibitors, MEK inhibitors) is allowed.

- 3.104 Age ≥ 18 years. Because no dosing or adverse event data are currently available on the use of trolizole in participants < 18 years of age, children are excluded from this study, but will be eligible for future pediatric trials.
- 3.105 ECOG performance status 0 or 1 (see Appendix A).
- 3.106 Participants must have adequate organ and marrow function as defined below:
- absolute neutrophil count $\geq 1,000/\text{mcL}$
 - total bilirubin $\leq 1.5 \times$ institutional upper limit of normal (ULN), or in the case of Gilbert's disease $\leq 3 \times$ ULN
 - AST(SGOT)/ALT(SGPT) $\leq 3 \times$ institutional ULN
- 3.107 Human immunodeficiency virus (HIV)-infected participants on effective anti-retroviral therapy with undetectable viral load within 6 months are eligible for this trial.
- 3.108 For participants with evidence of chronic hepatitis B virus (HBV) infection, the HBV viral load must be undetectable on suppressive therapy, if indicated.
- 3.109 Participants with a history of hepatitis C virus (HCV) infection must have been treated and cured. For participants with HCV infection who are currently on treatment, they are eligible if they have an undetectable HCV viral load.
- 3.110 Participants with known history or current symptoms of cardiac disease, or history of treatment with cardiotoxic agents, should have a clinical risk assessment of cardiac function using the New York Heart Association Functional Classification. To be eligible for this trial, participants should be class 2B or better.
- 3.111 The effects of trolizole on the developing human fetus are unknown. For this reason and because ipilimumab is a pregnancy category C, women of child-bearing potential and men must agree to use adequate contraception (hormonal or barrier method of birth control; abstinence from heterosexual intercourse) prior to study entry, for the duration of study participation, and 4 months after completion of all study drugs. Should a woman become pregnant or suspect she is pregnant while she or her partner is participating in this study, she should inform her treating physician immediately. Men treated or enrolled on this protocol must also agree to use adequate contraception prior to the study, for the duration of

study participation, and 4 months after completion of all study drugs.

3.112 Ability to swallow pills.

3.113 Ability to understand and the willingness to sign a written informed consent document.

3.2 Exclusion Criteria

3.201 Ocular subtype of melanoma.

3.202 Cytologically confirmed leptomeningeal metastases, or convincing imaging evidence of leptomeningeal spread.

3.203 Prior whole brain radiation therapy (WBRT).

3.204 Prior combination therapy with concurrent ipilimumab (3 mg/kg IV) + nivolumab (1 mg/kg IV) in the 24 months prior to the date of registration.

3.205 Participants who have had systemic therapy (immunotherapy, chemotherapy, or targeted therapy), or major surgery within 3 weeks prior to the date of registration. Participants who have had radiotherapy within 10 days prior to the date of registration.

3.206 Participants who require immediate local treatment (surgical resection or radiosurgery) of brain metastases due to neurologic symptoms, or brain metastases located in sensitive areas of the brain requiring immediate local treatment.

3.207 Participants who have required systemic steroids to manage neurologic symptoms (seizures, cerebral edema, severe headache, nausea/vomiting, etc.) within 1 week prior to the date of registration.

3.208 Participants who are receiving any other investigational agents for cancer or neurologic disease.

3.209 Extreme claustrophobia that would interfere with performing brain MRIs or severe allergy to gadolinium contrast.

3.210 History of severe or life-threatening allergic reactions attributed to compounds of similar chemical or biologic composition to trolizole, riluzole, ipilimumab, or nivolumab.

3.211 Second primary malignancy that is a competing cause of death in the opinion of the treating investigator (prognosis < 6 months).

- 3.212 Patients with a history of solid organ transplant, or allogeneic bone marrow transplant.
- 3.213 Active autoimmune disease or any other condition requiring systemic treatment with either corticosteroids (>10 mg daily prednisone equivalents) or other systemic immunosuppressive medications within 3 weeks of registration.
- 3.214 History of grade 4 immune related adverse event from prior cancer treatment, (with the exception of asymptomatic elevation of serum amylase or lipase).
- 3.215 History of immune-related adverse event from prior cancer immunotherapy treatment that has not improved to grade 0-1 (with the exception of patients with ongoing thyroid, adrenal or gonadal insufficiency requiring continued medical treatment, vitiligo, or asymptomatic elevation of serum amylase or lipase).
- 3.216 Participants receiving any medications or substances that are inhibitors or inducers of the liver enzyme Cytochrome P-450 CYP1A2, including fluvoxamine, cimetidine, amiodarone, efavirenz, fluoroquinolones (including ciprofloxacin and levofloxacin), fluvoxamine, furafylline, interferon, methoxsalen, mibefradil, or ticlopidine. These medications must be discontinued at least 7 days prior to registration.
- 3.217 Participants with uncontrolled intercurrent illness.
- 3.218 Participants with psychiatric illness/social situations that would limit compliance with study requirements.
- 3.219 Pregnant and nursing (breastfeeding) women are excluded from this study because the effects of troriluzole on the developing human fetus are unknown, and because ipilimumab is pregnancy category C.

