2.4 Troriluzole

i. Overview

Mechanism of action. Troriluzole (formerly known as FC-4157, BHV-4157, and trigriluzole) is an investigational tri-peptide prodrug of riluzole with improved PK/PD properties. Riluzole was FDA-approved for ALS in 1995. The mechanism of action of troriluzole, which is rapidly cleaved into riluzole, is not fully understood, is thought to be entirely due to the action of riluzole which blocks the release of glutamic acid and up-regulates the excitatory amino acid transporter EAAT2. Interruption of GRM1-mediated signaling by limiting the available ligand, glutamate, leads to intracellular build-up of glutamate. The build-up decreases the exchange of glutamate and cystine, which limits the availability of cysteine, a key component of L-Glutathione (GSH) synthesis. This process results in reduced intracellular GSH and enhanced cellular stress, genome instability and DNA damage.

Pharmacologic advantages. Blood levels of riluzole are highly variable upon oral administration of riluzole due to its metabolism by a particular cytochrome P450 enzyme, Cyp1A2, which is variably expressed. We have discovered a novel Type IIb prodrug of riluzole, troriluzole, that minimizes this variable metabolism, readily releases the drug riluzole into the blood stream when given orally to mice, rats, cynomolgus monkeys and humans and is >20X more potent than riluzole itself in a mouse melanoma xenograft model.

Highlights of the prodrug troriluzole include:

- Troriluzole is stable in simulated gastric fluid (SGF) and simulated intestinal fluid with stability half-lives of >60 and 98 min respectively.
- Troriluzole has adequate solubility (247 ug/mL) in a standard aqueous oral delivery vehicle (aqueous 2% Tween 80/0.5% methylcellulose) and high cellular permeability with no efflux potential.
- Troriluzole is highly stable in mouse (MLM) and human (HLM) liver microsomes with half-lives greater than 1 h in both species. Riluzole is metabolized to N-hydroxyriluzole in HLM containing high activity Cyp1A2 with a half-life of <30 min, but is stable to HLM with low activity of Cyp1A2.

- Troiriluzole is actively transported by the PepT1 transporter.

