Given the hypothesis that troriluzole treatment inhibits GRM1 signaling, thereby inhibiting release of exosomes, decreasing TAMs, and allowing lymphocytes into the tumor-stromal interface, and the compelling preclinical data the troriluzole enhances the antitumor activity of PD-1 immune checkpoint inhibitor, a phase Ib trial was conducted at a single site. The combination of troriluzole and nivolumab was found to be well tolerated. We enrolled 14 patients with advanced solid tumors (melanoma = 3, NSCLC = 3, renal cell cancer = 2, NSCLC = 2, head and neck cancer = 2). Eleven patients had prior therapy with anti-PD-1 or anti-PD-L1. Patients were exposed to troriluzole doses from 140mg to 560mg total daily dose. Dose limiting toxicities (DLT) occurred in 3 patients which were characterized as 1) intolerable nausea in a patient who was subsequently diagnosed with brain metastases 2) grade 3 fatigue and 3) atrial fibrillation. No patient required more than one dose reduction. PK sampling demonstrated that the prodrug was cleaved efficiently without regard to food. The most common TEAEs (all grades) occurring in > 40% of patients were transaminitis, increased lipase and nausea. DLT occurred in 3 patients: 1) grade 3 anorexia, 2) grade 3 fatigue and, 3) atrial fibrillation. The MTD was determined to be troriluzole 140 mg QAM + 280 mg PO QPM. The response rate was 7 % (1/14); this occurred in a PD-L1 treated patient. The 6-month PFS rate was 21%.³⁰

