5.2 Pre-Treatment Criteria

Safety Run-In and Randomized Treatment:

Cycle 1, Day 1. The subject must meet all eligibility criteria on Day 1. Baseline laboratory and clinical evaluations are to be conducted within 1 week prior to start of protocol therapy. If the participant's condition is deteriorating, evaluations should be repeated within 48 hours prior to initiation of therapy. Complete blood count with differential and comprehensive metabolic panel results should be reviewed prior to treatment. It is recommended that participants receive all indicated routine immunizations prior to the start of treatment (due to possible effect on immunologic correlative science and desire to minimize toxicity during the induction phase).

Subsequent Cycles. Safety assessments, including complete blood count with differential and comprehensive metabolic panel results must be performed prior to administration of any study agent, excluding oral therapy, which is continuous. Study assessments and agents should be administered within + 7 days of the protocol-specified date for Days 1-309, and within + 14 days of the protocol-specified date for Days 337-673.

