5.5 Concomitant Medication and Supportive Care Guidelines

Safety Run-In and Randomized Treatment:

Acceptable Concomitant Medications. All treatments that the investigator considers necessary for a subject's welfare may be administered at the discretion of the investigator in keeping with the community standards of medical care. All concomitant medication will be recorded on the case report form (CRF) including all prescription, over-the-counter (OTC), herbal supplements, and IV medications and fluids.

Selected acceptable medications include:

- Antiepileptic (anti-seizure, anticonvulsant) medications. *Exception:* Carbamazepine, which is a CYP1A2 inducer, is prohibited.

- Erythropoietin
- Hormone replacement therapy
- Immunizations. Routine vaccinations are permitted but discouraged during Days 1-84 when the most toxicity is expected. If the treating investigator feels that a vaccination is unsafe to delay (e.g. seasonal influenza immunization), the patient may receive the vaccination during Days 1-84. Vaccinations received during the study period should be documented as a concomitant medication.
- Anticoagulation. Prophylactic or treatment-dose anticoagulation is permitted when indicated. ASCO has recently published new a guideline on venous thromboembolism prophylaxis and treatment in patients with cancer. Intracranial or CNS bleeding within the past 4 weeks is considered a relative contraindication to therapeutic anticoagulation.³⁷
- Steroids (dexamethasone, prednisone, etc.) – allowable indications
 - During study participation, neurologic symptoms may arise or worsen. Steroids may be used to control neurologic symptoms. Steroid treatment ≤ 16 mg dexamethasone PO daily tapered in ≤ 4 weeks is allowed for the treatment of brain edema (single episode). If a second episode of brain edema requires steroid treatment, the Sponsor-Investigator must be consulted.
 - Systemic steroids may be used for treatment of irAEs.
 - A brief course (< 7 days) of corticosteroids for prophylaxis of side effects from SRT is permitted.
 - A brief course (< 7 days) of corticosteroids for prophylaxis (e.g., contrast dye allergy) or for treatment of non-autoimmune conditions (e.g., delayed-type hypersensitivity reaction caused by contact allergen) is permitted.
 - Intranasal, intra-articular, and inhaled steroids are acceptable for any indication.

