 - NOTE: Patients who receive systemic corticosteroids for any reason (including toxicity or management of symptoms brain metastases) must be off corticosteroids or have tapered down to an equivalent dose of prednisone 10 mg/day (dexamethasone ≤ 1.5 mg PO daily) or less to continue immune checkpoint therapy.

Prohibited Medications

- Systemic steroids for indications other than the indications above
- No investigational or commercial agents or therapies other than those described below may be administered with the intent to treat the patient's malignancy.
- Prophylactic use of colony stimulating factors (CSFs) are not permitted. They may be needed for supportive care and should be discontinued when the event resolves/improves. If needed longer than 4 weeks, the subject must discontinue study treatment.
- IVIG

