Treatment-related Adverse Event	Grade of Event	Nivolumab or Nivolumab/Ipilimumab
Pneumonitis, broncho-spasm, pulmonary toxicity or interstitial lung disease	≤ Grade 1	No dose modification.
	Grade 2	Hold dose pending evaluation. Consider pulmonary and/or ID consultation. Resume if an alternative diagnosis is rendered.
	Grade 3	Off nivolumab and/or ipilimumab treatment
	Grade 4	Off nivolumab and/or ipilimumab treatment
	Above does not include infusion reactions.	
Distinguishing inflammatory pneumonitis is often a diagnosis of exclusion for patients who do not respond to antibiotics and have no causal organism identified including influenza. Most patients with respiratory failure or hypoxia will be treated with steroids. Bronchoscopy may be required and analysis of lavage fluid for lymphocytic predominance may be helpful. Patients with new lung nodules should be evaluated for sarcoid like granuloma. Please consider recommending seasonal influenza killed vaccine for all patients.		
Thrombocytopenia	≤ Grade 1	No dose modification
	Grade 2	Hold until ≤ Grade 1 OR baseline (exceptions as noted below) ¹
	Grade 3	Off nivolumab and/or ipilimumab treatment
	Grade 4	Off nivolumab and/or ipilimumab treatment
Neutropenia	≤ Grade 1	No dose modification
	Grade 2	Hold until ≤ Grade 1 OR baseline (exceptions as noted below) ¹
	Grade 3	Off nivolumab and/or ipilimumab treatment
	Grade 4	Off nivolumab and/or ipilimumab treatment
Renal	≤ Grade 1	No dose modification
	Grade 2	Hold until ≤ Grade 1 (or baseline)
	Grade 3	Off nivolumab and/or ipilimumab treatment
	Grade 4	Off nivolumab and/or ipilimumab treatment
Endocrine Hypophysitis Adrenal Insufficiency	≤ Grade 1	No dose modification
	Grade 2	Hold until patients are on a stable replacement hormone regimen. If treated with steroids patients must be stable off steroids for two weeks.
	Grade 3	Hold until patients are on a stable replacement hormone regimen. If treated with steroids patients must be stable off steroids for two weeks.
	Grade 4	Off nivolumab and/or ipilimumab treatment

Treatment-related Adverse Event	Grade of Event	Nivolumab or Nivolumab/Ipilimumab

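### CYP1A2 inhibitors and inducers are excluded at entry (3.216), but apart from carbamazepine Section 5.5 does not restrict starting them during troriluzole/placebo dosing

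*Combined protocol and SAP*

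**What the plan says.** **At entry.** Item 3.216 in Section 3.2 excludes anyone taking a CYP1A2 inhibitor or inducer. It names, among others, fluvoxamine, cimetidine, amiodarone, interferon and the fluoroquinolones ciprofloxacin and levofloxacin, and adds "These medications must be discontinued at least 7 days prior to registration". Section 5.2 repeats the check at the start of dosing: "The subject must meet all eligibility criteria on Day 1". For later cycles, 5.2 asks for safety assessments only.

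**On treatment.** Section 5.5 opens with a permissive rule: "All treatments that the investigator considers necessary for a subject's welfare may be administered at the discretion of the investigator". Antiepileptics are acceptable with one exception: "Carbamazepine, which is a CYP1A2 inducer, is prohibited". The list of prohibited medications covers four things: systemic steroids outside the listed indications, other anticancer treatment ("No investigational or commercial agents or therapies other than those described below may be administered with the intent to treat the" malignancy), prophylactic colony stimulating factors, and IVIG. It has no CYP1A2 entry.

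**Pharmacology.** Section 2.4 puts the variable blood levels of oral riluzole down to CYP1A2 metabolism and reports "Riluzole is metabolized to N-hydroxyriluzole in HLM containing high activity Cyp1A2 with a half-life of <30 min". The same section says that troriluzole reduces this variability, and 7.1 says that it bypasses first-pass metabolism. Section 8.1 does not expect P450 inhibitors to affect the prodrug much, and notes that no clinical interaction studies have yet been done.

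**The concern.** The plan screens out an exposure at the door and then permits it from the day after the Day 1 check until the last oral dose (Day 337 in 5.4). The carbamazepine ban shows that CYP1A2 was considered relevant during dosing, yet the rule reaches only one drug. The documents give no reason for treating the rest of the class differently.

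Two things are at stake. The first is patient safety: an inhibitor would be expected to raise riluzole exposure and an inducer to lower it, and 7.1 describes dizziness, somnolence, nausea and transaminase effects as dose related. The second is a clean reading of the run-in. Under 6.2, a listed grade 2 neurologic event lasting 4 days or more, judged at least possibly related to troriluzole, is a DLT, and 6.2 makes no provision for an interacting co-medication. Two DLTs in a cohort lead to de-escalation or stopping (5.1.1). That direction protects patients, but it could carry a lower dose than necessary into Part II.

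**Working it through.** This is a check of the text. The plan states no figure on this point that could be reproduced.

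1. **How far the entry rule reaches.** 3.216 is tied to registration by its 7-day washout, and 5.2 extends it to Cycle 1 Day 1. Neither section applies it afterwards.

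2. **Whether another section continues it.** Section 5.5 has the carbamazepine exception and no class rule. Sections 6.1 and 6.3 set hold and resumption rules that do not mention CYP1A2. Section 8.1 discusses interactions but gives no instruction. The study calendar in Section 10 adds none.

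3. **What can therefore be started.** Ciprofloxacin, levofloxacin, cimetidine, fluvoxamine and amiodarone all fall under the general permission in 5.5. Interferon, also named in 3.216, is barred on treatment only if it is given for the melanoma.

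4. **Whether the need is foreseeable.** Table 6.1 in Section 6.4 says "Distinguishing inflammatory pneumonitis is often a diagnosis of exclusion for patients who do not respond to antibiotics", so antibiotic courses are anticipated. Section 2.4 lists among the phase Ib DLTs "2) grade 3 fatigue and 3) atrial fibrillation". The documents do not say which antibiotic or antiarrhythmic would be used.

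5. **Whether 8.1 settles the pharmacology.** Its statement concerns the prodrug and P450 inhibitors. It does not address inducers, or the riluzole released after cleavage, which 2.4 describes as a CYP1A2 substrate.

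6. **Whether exposure matters.** Section 7.1 reports dizziness in 2.5% on placebo, 5.1% at riluzole 50 mg/day, 3.8% at 100 mg/day and 12.7% at 200 mg/day. The corresponding figures for somnolence are 1.3%, 0.8%, 1.9% and 4.1%. Marked ALT elevations exceeded placebo at 100 and 200 mg/day. These figures show that exposure matters at the upper end. They do not measure an interaction, because the documents do not say how far any listed agent would shift riluzole exposure after troriluzole.

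7. **What a hold would cost in the run-in.** Inputs: a 6-week DLT period and an 80% dose rule (5.1.1), twice-daily dosing, and a first dose on the evening of Day 1 (5.3).
   - Scheduled doses: 42 × 2 − 1 = 83
   - Doses needed: 0.80 × 83 = 66.4, so 67
   - Doses that may be missed: 83 − 67 = 16, or 16 / 2 = 8 days

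   With no other missed doses, a hold of more than about 8 days means the participant cannot count as having completed the DLT period without toxicity.

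**The case against.** The strongest reply is that existing rules already cover much of the exposure.

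- Section 6.7 lists pneumonia and decreased lung function among the shared adverse events, usually attributed to all three drugs. Section 6.3 requires a hold for related events of grade 2 or higher. For many lung events, troriluzole would already be stopped when antibiotics begin. The same holds for atrial fibrillation of grade 2 or higher judged related to troriluzole.
- Section 6.1 allows interruptions for medical events unrelated to study therapy, so an investigator who needs a listed agent may hold the capsules without a protocol violation.
- Sections 2.4, 7.1 and 8.1 all suggest less metabolic sensitivity than with oral riluzole.
- Concomitant medication is recorded on the CRF, and the Investigational Drug Brochure, not available here, may give guidance.

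All of this stands, and it narrows the gap without closing it. Unrelated and grade 1 events are not covered. A hold under 6.3 ends when the toxicity improves, whether or not the interacting drug has stopped. Section 6.1 permits an interruption but does not ask for one. Recording use does not limit it.

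Three stronger readings are tempting, and the documents support none of them:

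- **A figure for the run-in.** A reader might calculate how much likelier the starting dose is to be abandoned once one interaction-caused DLT has been counted. That presupposes the event, and the result would be the same for a first DLT of any cause. It does not measure this gap, and the documents give no rate for such events.
- **Bias in global PFS.** Nothing in the documents shows how many participants would receive a listed agent, or that their PFS would change.
- **A large interaction.** No clinical interaction data exist, and the protocol's own statements point towards a modest effect.

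**Conclusion.** The inconsistency is real and deserves correction. CYP1A2 inhibitors and inducers are barred as a class through Cycle 1 Day 1. After that, every agent except carbamazepine is open to the investigator's discretion, apart from anticancer use. This goes beyond a missing detail, because the permissive rule in 5.5 allows what 3.216 excludes.

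Neither the number of participants affected nor the change in exposure can be derived, and both may be small. The conclusion rests on the text of the two sections, on riluzole being a CYP1A2 substrate (2.4), and on its dose-related toxicity (7.1). It assumes that the brochure does not already bind sites to an on-treatment restriction. Investigator attribution, holds for related events and the run-in safety review limit the harm. No effect on the primary endpoint, sample size or error rates is claimed.

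**What to change.** Add to the prohibited medications in 5.5: 'CYP1A2 inhibitors and inducers (see 3.216) should be avoided through the last dose of troriluzole/placebo, in both arms; use an unlisted alternative where one exists. If use is unavoidable, consult the Sponsor-Investigator, who may interrupt the oral study drug under 6.1 or continue it with closer monitoring of neurologic AEs and LFTs; record the agent and dates on the CRF.'

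Add to 8.1 that released riluzole is metabolized by CYP1A2, with a pointer to 3.216 and 5.5.

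An avoid-or-consult rule is preferable to a flat ban with a compulsory hold. A participant who needs long-term amiodarone would exceed the 6-week hold limit and be removed from the study under 6.3, whereas the proposed wording lets dosing continue with monitoring. No exemption from the dose-reduction rule in 6.3 should be needed, since that scheme concerns related adverse events and these interruptions fall under 6.1.

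The change costs a few lines of wording, with no added participants and no routine visits. The choice of antibiotic and antiarrhythmic becomes somewhat narrower. In the run-in, an interruption of more than about 8 days would fail the 80% dose rule, and the Sponsor-Investigator should weigh this when choosing between holding and monitoring.
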